8. STATISTICAL ANALYSIS

The mean data before and after treatment will be tested for homogeneity and normality. In order to draw parallels between the two data sets, parametric measurements will be considered using the T-test for data with normal distribution, while data with abnormal distribution will be analyzed using a non-parametric test, namely the Wilcoxon test. The statistical analysis of all data will be conducted using SPSS version 20.0.

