1. PROTOCOL RESUME

1.1. Protocol Resume

Protocol title:

Effect of White Tea (*Camellia sinensis* L.) Beverages on Anthropometric, Hematological, Biochemical and First Line Antioxidant Enzymes Activity of Healthy Human (Superoxide Dismutase, Catalase, and Glutathione Peroxidase)

Research aims:

Understanding the potential of white tea for human health in terms of anthropometry (body weight, body mass index and waist circumference), blood pressure and biochemistry (lipid profile, blood glucose levels and antioxidant enzyme activity). Furthermore, the safety of white tea products will be evaluated by means of haematological parameters (red blood cells, haematocrit, haemoglobin, mean corpuscular volume (MCV), and mean corpuscular haemoglobin (MCH)), liver parameters (alanine aminotransferase (ALT) and aspartate aminotransferase (AST)), and renal parameters (creatinine levels, estimated glomerular filtration rate (eGFR), and blood urea nitrogen) following a 14-day period of white tea consumption.

Study design:

This study will combine a pilot study with a pre-post quasi-experimental design.

Specific aims

1. Determine the effect of white tea consumption on the anthropometry of healthy subjects based on body weight, body mass index, waist circumference, and blood pressure.
2. Determine the effect of white tea consumption on the biochemical parameters of healthy subjects based on blood glucose, lipid profile (total cholesterol, low-density lipoprotein (LDL), high-density lipoprotein (HDL), and triglycerides), alanine aminotransferase (ALT), aspartate aminotransferase (AST), serum creatinine levels, estimated glomerular filtration rate (eGFR), and urea nitrogen levels.
3. Determine the effect of white tea consumption on blood parameters in healthy subjects based on red blood cell count, haemoglobin, haematocrit, mean corpuscular haemoglobin (MCH), and mean corpuscular volume (MCV).
4. Determine the effect of white tea consumption on the activity of first-line antioxidant enzymes (superoxide dismutase, catalase, and glutathione peroxidase) in healthy subjects.

Pre-post quasi-experimental study design

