All data pertaining to the study will be stored on CRFs/individual screening sheets. The data will be recorded in both soft and hard file formats on a daily basis.

Evaluation Criteria

Anthropometric measurements, blood pressure, haematology, and biochemistry tests will be conducted before the intervention and one day after the last intervention (day 0 and day 15). Anthropometric measurements, blood pressure, and blood sampling will be conducted at the Faculty of Pharmacy, Padjadjaran University. The biochemical examinations will be carried out at the clinical laboratory of the Bandung City Health Office, while the complete haematology and antioxidant enzyme examinations will be carried out at the Biomedical Laboratory of the Faculty of Medicine, Padjadjaran University. The results of the examinations conducted before and after the white tea intervention will be analyzed to ascertain the effect of white tea consumption over a period of 14 days. The types of food and beverages consumed by the research subjects and their daily activities were recorded in the CRF for a period of 28 days (from the wash-out phase to the observational phase).

Statistical Analysis

The effect of white tea administration will be compared before and after treatment using a t-test analysis.

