7.5. Respondent Monitoring

Monitoring of anthropometry and blood pressure

The subjects of the research will undergo physical monitoring, including weight, height, BMI, waist circumference and blood pressure, by research team on days 0 and 15 (one day before and one day after the last day of the white tea intervention).

Laboratory monitoring

Laboratory monitoring was conducted on days 0 and 15 (one day before and one day after the last day of the white tea intervention) on blood samples from subjects in order to determine the effects of drinking tea for a period of 14 days. Should the preliminary investigative results pertaining to haematological parameters (RBC, HB, HCT, MCV and MCH), ALT, AST, serum creatinine levels, eLFG and urea nitrogen levels demonstrate abnormality, the subject will be withdrawn from the study for reasons of safety. Haematological tests are performed to ensure that the subject is not anaemic. ALT and AST tests are performed to ensure that there is no liver dysfunction, while serum creatinine, eGFR, and urea nitrogen tests are performed to ensure that the subjects do not have kidney dysfunction. In summary, the parameters employed in this study to observe the effects of white tea consumption are outlined as follows:

- a. Hematology profile
- b. Lipid profil
- c. Fasting blood glucose
- d. ALT dan AST
- e. Serum creatinine level, urea nitrogen level and eGFR
- f. First line antioxidant enzymes (SOD, CAT dan GPx).

Monitoring consumption and daily activities

In order to ensure that respondents adhere to the prescribed dietary regime, researchers will ensure that subjects abstain from the consumption of particular products that must be avoided during the course of the research process. Researchers will record all food and beverages consumed, the subjects' daily activities, and any complaints that may be experienced by the subjects, whether related or unrelated to the administration of white tea products.

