7.12. Antioxidant Enzymes Analysis

Antioxidant enzyme activity testing will be conducted at the Biomedical Laboratory, Faculty of Medicine, Padjadjaran University. Enzyme activity analysis will be performed on human blood serum collected on days 0 and 15. The analysis of antioxidant enzyme activity encompasses the assessment of superoxide dismutase (SOD), catalase (CAT) and glutathione peroxidase (GPx) activity. The analysis procedure will refer to the manual guideline in the Elabscience KIT.

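### Section 8 checks normality on the before and after values, but the data are paired and the check belongs on the within-subject differences

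*Combined protocol and SAP*

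**What the plan says.** Section 8 is the analysis plan. It opens: "The mean data before and after treatment will be tested for homogeneity and normality". For the parametric branch it states that "parametric measurements will be considered using the T-test for data with normal distribution". The alternative branch, for outcomes that fail the normality check, is worded separately: "while data with abnormal distribution will be analyzed using a non-parametric test, namely the Wilcoxon test". The Statistical Analysis line of Section 1.1 is shorter and names only one test: "The effect of white tea administration will be compared before and after treatment using a t-test analysis".

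The design is one group measured twice. Section 1.1 states: "This study will combine a pilot study with a pre-post quasi-experimental design". Section 7.5 states: "Laboratory monitoring was conducted on days 0 and 15". Section 7.12 states: "Enzyme activity analysis will be performed on human blood serum collected on days 0 and 15". Section 7.7 puts anthropometry on the same two days, and Section 7.8 ties blood pressure to the blood sampling days.

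In the text available, no section calls either test paired, says signed-rank, or mentions within-subject differences. No section says what follows from the homogeneity result.

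**The concern.** With each subject measured twice, the paired t-test uses only the change per subject, and the distribution of those changes decides whether it is the suitable test. Normal before and after values do not guarantee normal changes, and skewed values do not rule them out. A selection rule driven by the two sets of values can therefore pick the less suitable test in either direction. The rule governs every outcome: the antioxidant enzymes, lipids, glucose and anthropometry, and also the liver, kidney and blood parameters used to judge safety.

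Two wording points are secondary. T-test and Wilcoxon test each have a paired and an independent-samples form, and the plan does not say which. Equal variance before and after is not an assumption of a paired test, so the homogeneity test has no role.

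**Working it through.** **1. The plan's own figure.** The table in Section 6 gives 15 for a medium standardised difference in the 90% column. With 20% dropout, 15 / (1 − 0.20) = 18.75, rounded up to 19. This reproduces the stated sample size, and nothing below changes it. The checks use n = 19 (all subjects) and n = 15 (after dropout).

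**2. What the paired t-test uses.** With D = day 15 minus day 0 for each subject, t = mean(D) / (s_D / √n) on n − 1 df, where s_D² = s_0² + s_15² − 2·r·s_0·s_15. Equality of s_0 and s_15 is not required.

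A check on the after values hardly sees the changes. If baseline SD is k times the scale of the change, and the change has variance v on that scale, the change supplies v / (k² + v) of the after variance:
- normal change (v = 1), k = 3: 1/10 = 10%
- t with 3 df (v = 3), k = 10: 3/103 = 2.9%

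**3. The check misleads in both directions.** Assumed cases, Shapiro-Wilk at 5%, 4,000 runs:
- Skewed values, normal differences: the before/after check rejects in 47% (n = 15) and 59% (n = 19) of runs, against about 5% on the differences. The resulting loss of power is about 1 to 2 points.
- Near-normal values, skewed differences: the before/after check rejects in about 8% of runs, against 42% (n = 15) and 55% (n = 19) on the differences.

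**4. Power when changes are symmetric about the shift.** The documents give no distribution, SD or correlation, so the settings are assumed. Both rules use paired tests, two-sided 5%. The present rule is read as Wilcoxon if either the before or the after set fails Shapiro-Wilk. The alternative uses Wilcoxon if the differences fail. Baseline is normal with SD k times the scale of the change; shifts are on that scale. There were 40,000 trials per setting (simulation SE at most 0.25 points). Ranges are over k = 3 and 5 for the first two rows, and k = 3, 5 and 10 for the rest.

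| Changes | Shift | n | Present rule | Check on differences | Loss (points) |
|---|---|---|---|---|---|
| Normal | 0.8 | 19 | 90.9–91.0% | 90.9–91.1% | 0.0–0.1 |
| t, 10 df | 0.85 | 19 | 87.6% | 88.2% | 0.6 |
| t, 5 df | 0.9 | 19 | 83.0–83.4% | 85.3–85.7% | 2.3 |
| t, 3 df | 1.0 | 19 | 76.7–78.4% | 83.4–83.7% | 5.3–6.7 |
| t, 3 df | 1.0 | 15 | 68.8–69.8% | 73.3–73.9% | 4.1–4.9 |
| t, 2 df (extreme) | 1.0 | 19 | 60.3–64.7% | 73.7–73.9% | 9.2–13.4 |

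Lognormal values with correlation 0.8 (log-SD 0.2 or 0.5) gave losses between −0.5 and +0.3 points. With no shift, rejection in all these settings was 3.6–5.0% under the present rule and 4.8–5.2% with the check on differences.

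**5. Skewed changes.** These break the pattern. With exponential differences of true mean zero, normal baseline and n = 19, rejection was about 8% under the present rule and about 12% with the check on differences. Chi-square (3 df) differences gave 7.0% and 9.7% (8,000 runs). Both rules exceed 5% as tests of the mean. The check on differences exceeds it by more because it moves to the signed-rank test when skew is detected, and that test does not test the mean. For a mean shift of 0.5 with exponential differences at n = 19, power was 58% (present) against 45% (differences), and 58% against 68% with the skew reversed (3,000 runs).

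**6. Matching the interval to the test.** Where the differences fail Shapiro-Wilk and a shift exists, a t-based 95% CI and the signed-rank p-value disagree at 5% in 5–7% (normal), 16–17% (t, 5 df) and 22–24% (t, 3 df) of those outcomes. The exact Hodges-Lehmann interval disagreed in 0 of 20,000 trials per setting. That result is for continuous data; ties and zero differences were not covered.

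**The case against.** A pre-post study of one group implies paired tests, and Wilcoxon is often short for signed-rank. This stands, and it reduces the missing word to a naming point. A reader might infer that an independent-samples test is planned, and that would be costly: assuming a standardised change of 0.5 at n = 19, paired against unpaired power is 54% against 27% at correlation 0.5, and 90% against 20% at correlation 0.8. No section prescribes that analysis, so these figures do not measure this point.

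The wording of Section 8 is loose, and step 4 needs a reading of it (Wilcoxon if either set fails). This stands in part. Before and after values are the natural reading, and differences are never mentioned.

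The losses that matter need heavy-tailed changes, and the subjects are healthy, aged 20–35 and screened to normal biochemistry. No figure in the documents suggests such tails. This stands: the size is conditional, and may be nil.

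Moving the check does not leave error rates unchanged when changes are skewed, and selecting a test from the data at n = 15 to 19 is itself open to criticism; prespecifying one paired test would be simpler. Both stand. Neither makes the before and after values the right variable to check.

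**Conclusion.** The normality check that selects the test is on the wrong variable. That follows from the text and the design and needs no simulation. The unnamed pairing and the unused homogeneity test are secondary wording points.

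The size rests on assumed distributions and on the stated reading of the present rule. At n = 19, with changes symmetric about the shift, the loss of power is 0 points for normal changes, about 2 to 3 for t with 5 df and 5 to 7 for t with 3 df, with type I error not above 5%. With skewed values and normal changes it is about 1 to 2 points. With skewed changes the effect on power can go either way.

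Three stronger readings are not supported:
- That harm is confined to heavy-tailed changes, or that false positives cannot rise. Step 5 contradicts both, so no general reassurance on type I error can be given for either rule.
- That the corrected check protects the test of the mean. Under skew it rejects a zero mean change more often than the present rule.
- That the sample size is affected. It remains 19.

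**What to change.** Replace the first two sentences of Section 8 with:

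> For each outcome the day 15 minus day 0 difference is computed for each subject, and normality is assessed on these differences (Shapiro-Wilk, 5%). If it is not rejected, the two-sided paired t-test at 5% is used; if it is rejected, the two-sided Wilcoxon signed-rank test at 5% is used, with zero differences and ties handled by the software default, which is reported. The mean difference with its 95% CI is reported for every outcome; where the signed-rank test is used, the Hodges-Lehmann estimate (pseudo-median) with its 95% CI is added and is the interval that matches the p-value, which is not read as a test of the mean change.

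This deletes the homogeneity test. In the Statistical Analysis line of Section 1.1, replace the phrase naming a t-test with: as set out in Section 8. That also removes the mismatch between a t-test alone there and two candidate tests in Section 8.

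The cost is one short passage and one phrase, with the same data and sample size; the Hodges-Lehmann interval may need a little extra analysis work. The downside is that the test is still selected from the data, as now, and with skewed changes a signed-rank result does not refer to the mean change.

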9. STORAGE OF FILES AND DATA

9.1. Data Collections

Paper-based CRFs (hard files) will be used to record data, with copies being made in the form of scanned files and stored in the researcher's personal Google Drive, with access restricted to the principal investigator. It is imperative that all CRFs are completed for each research subject. In order to reduce errors in filling out the forms and inconsistencies between the data in the CRF and the database, the data manager will validate the data as follows: by entering the numerical data twice into the database (double data entry), by rereading the comments written, or by entering the data once with 100% Quality Control (QC). In the event of any discrepancies, the resolution process will be initiated through the utilisation of a data clarification form, which must be signed by the researcher. It is imperative to note that the clarification sheet will be attached to the original CRF, thus serving as a crucial instrument for the rectification of any data that may be found to be inconsistent.

9.2. Source Document

Source documents encompass all clinical information, laboratory results (in their original form or as certified copies), observations or other clinical activities deemed necessary for the reconstruction and evaluation of clinical trials. It is imperative that all source documents are retained by the investigator. It is incumbent upon the investigator to ensure that auditors, ethics committees and other officials are permitted to view source documents when required.

9.3. File Management in Clinical Trial Sites

Researchers have an obligation to ensure that files are stored in accordance with GCP and ethical guidelines.

9.4. Data and File Storage

It is incumbent upon the principal investigators to retain research files and data for security purposes, as well as for the purposes of audit and inspection following the completion of the research. It is imperative that essential documents be retained for a period of no less than five years.

10. QUALITY CONTROL AND ASSURANCE

10.1. Procedures at the Research Site

Standard Operating Procedures will be established for all relevant clinical and laboratory activities to ensure the quality of the research. Subject compliance will be monitored throughout the study to ensure adherence to the established inclusion and exclusion criteria. Researchers are obliged to sign and date all examination results, thereby confirming that said results have been reviewed. Researchers may appoint assistants to assist with the execution of research and the supervision of research assistants. Nevertheless, the onus for the research remains with the researcher.

Prior to the initiation of the research process, ethical approval will be sought. Researchers must ensure that all personnel have been adequately briefed and trained on SA GCP, ICH-GCP, protocols and all procedures for research purposes.

10.2. Research Supervision

The principal investigator will be responsible for the validity of the data collected. The purpose of monitoring is threefold: firstly, to ensure that the human rights of research subjects are protected; secondly, to ensure that research data is accurate, complete and verifiable against source data; and thirdly, to ensure that clinical trials are conducted in compliance with protocols and do not violate the ethical principles as stated in the Declaration of Helsinki.

The supervisor will inquire with the researcher about any missing or unclear data. All questions are to be addressed without delay. The supervision notes will document the findings during the supervision process, the reasons for the visit, and the signatures of the supervisor and research team.

10.3. Management of Research Data

The management of research data will adhere to rigorous protocols. All research data obtained will be entered into a screening form in hard copy format, which will then be meticulously compiled into a folder for each research subject. Subsequent to the entry of data, the screening form will undergo scanning on the same day and uploading to Google Drive as a soft copy, with the objective of minimising data loss. It is imperative to note that access to Google Drive is strictly limited to the primary research team, a measure that is crucial to ensure the strict confidentiality of the research data.

10.4. Audit

The audit process will be carried out by the principal investigator to assess compliance with the protocol, GCP guidelines and ethical principles. The objective of the audit is to evaluate the quality of data in terms of accuracy, adequacy and consistency, and to ascertain whether the research has been conducted in accordance with existing guidelines. As stipulated by Good Clinical Practice (GCP), a comprehensive review of all documentation pertaining to the research will be conducted as part of the audit. The audit will involve a comparison of the source documents with the CRF, with the objective

of ensuring the accuracy and adequacy of the recorded information. This process will include the verification of any side effects that may have occurred.

11. ETHICS AND RESPONSIBILITY

11.1. Basic Principles

This research will be conducted in accordance with the ethical principles set out in the Declaration of Helsinki.

11.2. Independent Ethics Committee Assessment

This research protocol will be reviewed by the Ethics Committee, which is an independent institution, and the Ethics Committee's assessment notes will be kept by the research team. Researchers will ensure the accuracy and completeness of the notes to be submitted to the Ethics Committee.

11.3. Informed Consent

Prior to the initiation of the study, written consent will be obtained from the subject, subsequent to the provision of a comprehensive explanation of the study.

Prior to participation, the researcher will furnish the subject with comprehensive information regarding the study. Subsequent to the communication of salient information and the determination of the subject's comprehension of the explanation, the informed consent form can be endorsed by the subject, the researcher, and a witness.

It is incumbent upon the researcher to ensure that each subject is provided with a full explanation of the research. The Ethics Committee must undertake a thorough evaluation of both the research participation consent form and information sheet, prior to their approval.

The original informed consent form is retained in the CRF, with a copy being provided to the patient. An additional copy is maintained in the patient's medical records.

Compensation for research subjects' expenses during the study:

The researcher will assume financial responsibility for all costs associated with care, laboratory tests and medication.

12. CONFIDENTIALITY

The confidentiality of subjects involved in this study will be guaranteed by the research team and field doctors involved. Only the study number and initials will be written in the CRF. All correspondence related to subjects will use the study number and initials. The informed consent form will include a statement allowing the research team to view the source data for review purposes.

13. PUBLICATION POLICY

The results of this study are to be submitted for publication upon completion of the research, in the form of a joint publication with clinical researchers.

APPENDIX 1. SCREENING FORM FOR SUBJECTS

SAMPLE

Research Number:	Respondent's initials: [] [] []
------------------	------------------------------------

SCREENING 1 – PERSONAL DATA

PERSONAL DATA		Officer ()
Date of data collection	: [] / [] / [] (DD/MM/YY)	
Name / initial	: [] [] []	
Place and Date of Birth		
Age	: Tahun	
Gender	: Pria / Wanita *	
Job	:	
Address	:	
Contact	:	

Note: The first two boxes in the initials are filled in with the first two letters of the two words of the name, and the third box is filled in with the date of birth. If the date of birth contains two numbers, use only one of them.

Example: Name: [name], Date of Birth: Januari 8th → [L|C|8].

MEDICAL HISTORY

History	Yes	No	Unknown
Have you ever had anaemia within the last 5 years?			
Do you have a history of kidney disorder?			
Do you have a history of stomach ulcers or GERD?			
Do you have a history of liver disorder?			
Are you an active smoker < 5 years?			
Are there any family members who smoke?			
Are you undergoing any medical treatment? Please specify!			

Signature of officer after filling out form:

Initials:

Date:

SAMPEL

Research Number:	Respondent's initials: []
------------------	---

SCREENING 2 – ANTHROPOMETRY AND BLOOD PRESSURE

ANTHROPOMETRIC EXAMINATION (PRE)	
Body weight : kg	Body height : cm
BMI : kg/m ²	
Waist Circumference: cm	
BLOOD PRESSURE MEASUREMENT (PRE)	
Blood pressure:	

ANTHROPOMETRIC EXAMINATION (POST)	
Body weight : kg	Body height : cm
BMI : kg/m ²	
Waist Circumference: cm	
BLOOD PRESSURE MEASUREMENT (POST)	
Blood pressure:	

Signature of officer after filling out form: Initials: Date:

SAMPEL

Research Number:	Respondent's initials: []
------------------	----------------------------

SCREENING 3 – BLOOD AND BIOCHEMICAL TESTS

a. Initial Screening

Parameters	Test Date/Time	Result	Status
Hematology Profile	[] / [] / [] (DD/MM/YY) [] . [] WIB	RBC : $10^6/\mu\text{L}$ HB : g/dL HCT : % MCV : fL MCH : pg	 Eligible  Not Eligible
Lipid Profile	[] / [] / [] (DD/MM/YY) [] . [] WIB	TC : mmol/L HDL : mmol/L LDL : mmol/L Tg : mmol/L	 Eligible  Not Eligible
Fasting Blood Glucose	[] / [] / [] (DD/MM/YY) [] . [] WIB	mmol/L	 Eligible  Not Eligible
ALT	[] / [] / [] (DD/MM/YY) [] . [] WIB	$\mu\text{kat/L}$	 Eligible  Not Eligible
AST	[] / [] / [] (DD/MM/YY) [] . [] WIB	$\mu\text{kat/L}$	 Eligible  Not Eligible
Creatinine	[] / [] / [] (DD/MM/YY) [] . [] WIB	$\mu\text{mol/L}$	 Eligible  Not Eligible
eGFR	[] / [] / [] (DD/MM/YY) [] . [] WIB	$\text{mL/min}/1.73\text{m}^2$	 Eligible  Not Eligible
Ureum	[] / [] / [] (DD/MM/YY) [] . [] WIB	mmol/L	 Eligible  Not Eligible
Antioxidant enzymes	[] / [] / [] (DD/MM/YY) [] . [] WIB	SOD: CAT: GPx:	 Eligible  Not Eligible

Signature of officer after filling out form:

Initials:

Date:

SAMPEL

Research Number:	Respondent's initials: []
------------------	----------------------------

b. Final Screening

Parameters	Test Date/Time	Result	Status
Hematology Profile	[] / [] / [] (DD/MM/YY) [] . [] WIB	RBC : $10^6/\mu\text{L}$ HB : g/dL HCT : % MCV : fL MCH : pg	 Eligible  Not Eligible
Lipid Profile	[] / [] / [] (DD/MM/YY) [] . [] WIB	TC : mmol/L HDL : mmol/L LDL : mmol/L Tg : mmol/L	 Eligible  Not Eligible
Fasting Blood Glucose	[] / [] / [] (DD/MM/YY) [] . [] WIB	mmol/L	 Eligible  Not Eligible
ALT	[] / [] / [] (DD/MM/YY) [] . [] WIB	$\mu\text{kat/L}$	 Eligible  Not Eligible
AST	[] / [] / [] (DD/MM/YY) [] . [] WIB	$\mu\text{kat/L}$	 Eligible  Not Eligible
Creatinine	[] / [] / [] (DD/MM/YY) [] . [] WIB	$\mu\text{mol/L}$	 Eligible  Not Eligible
eGFR	[] / [] / [] (DD/MM/YY) [] . [] WIB	$\text{mL/min}/1.73\text{m}^2$	 Eligible  Not Eligible
Ureum	[] / [] / [] (DD/MM/YY) [] . [] WIB	mmol/L	 Eligible  Not Eligible
Antioxidant enzymes	[] / [] / [] (DD/MM/YY) [] . [] WIB	SOD: CAT: GPx:	 Eligible  Not Eligible

Signature of officer after filling out form: Initials: Date:

SAMPEL

Research Number:	Respondent's initials: []
------------------	---

SKRINING 4 – MAKANAN, MINUMAN, KEGIATAN HARIAN DAN KELUHAN

Day-	Food Intake	Beverages / Supplement	Daily activity/ Complaint
1	Breakfast: Lunch: Dinner:	 Fruit juice: Yes / No* Indicate yes if applicable:  Vitamin Yes / No* Indicate yes if applicable:	Sleep duration: Activity: Are you experiencing any of the following? (Please indicate when the symptoms began.)  Nausea  Vomiting  Constipation  Weakness  Loss of appetite  Fever  Excessive fatigue
2	Breakfast: Lunch: Dinner:	 Fruit juice: Yes / No* Indicate yes if applicable:  Vitamin Yes / No* Indicate yes if applicable:	Sleep duration: Activity: Are you experiencing any of the following? (Please indicate when the symptoms began.)  Nausea  Vomiting  Constipation  Weakness  Loss of appetite  Fever  Excessive fatigue
3	Breakfast: Lunch:	 Fruit juice: Yes / No* Indicate yes if applicable:  Vitamin Yes / No*	Sleep duration: Activity: Are you experiencing any of the following? (Please indicate when the symptoms began.)  Nausea

Signature of officer after filling out form:

Initials:

Date:

SAMPLE

Research Number:		Respondent's initials: []	
	Dinner:	Indicate yes if applicable:	 Vomiting  Constipation  Weakness  Loss of appetite  Fever  Excessive fatigue
4	Breakfast:	 Fruit juice: Yes / No* Indicate yes if applicable:	Sleep duration: Activity:
	Lunch:	 Vitamin Yes / No* Indicate yes if applicable:	Are you experiencing any of the following? (Please indicate when the symptoms began.)  Nausea  Vomiting  Constipation  Weakness  Loss of appetite  Fever  Excessive fatigue
	Dinner:		
5	Breakfast:	 Fruit juice: Yes / No* Indicate yes if applicable:	Sleep duration: Activity:
	Lunch:	 Vitamin Yes / No* Indicate yes if applicable:	Are you experiencing any of the following? (Please indicate when the symptoms began.)  Nausea  Vomiting  Constipation  Weakness  Loss of appetite  Fever  Excessive fatigue
	Dinner:		
6	Breakfast:	 Fruit juice: Yes / No* Indicate yes if applicable:	Sleep duration: Activity:
			Are you experiencing any of the following? (Please

Signature of officer after filling out form:

Initials:

Date:

SAMPLE

Research Number:		Respondent's initials: []	
	Lunch: Dinner:	 Vitamin Yes / No* Indicate yes if applicable:	indicate when the symptoms began.)  Nausea  Vomiting  Constipation  Weakness  Loss of appetite  Fever  Excessive fatigue
7	Breakfast: Lunch: Dinner:	 Fruit juice: Yes / No* Indicate yes if applicable:  Vitamin Yes / No* Indicate yes if applicable:	Sleep duration: Activity: Are you experiencing any of the following? (Please indicate when the symptoms began.)  Nausea  Vomiting  Constipation  Weakness  Loss of appetite  Fever  Excessive fatigue
8	Breakfast: Lunch: Dinner:	 Fruit juice: Yes / No* Indicate yes if applicable:  Vitamin Yes / No* Indicate yes if applicable:	Sleep duration: Activity: Are you experiencing any of the following? (Please indicate when the symptoms began.)  Nausea  Vomiting  Constipation  Weakness  Loss of appetite  Fever  Excessive fatigue
9	Breakfast:	 Fruit juice: Yes / No*	Sleep duration: Activity:

Signature of officer after filling out form:

Initials:

Date:

SAMPLE

Research Number:	Respondent's initials: []
------------------	---

	
Lunch:
 
Dinner:
	
Indicate yes if applicable:
 
 Vitamin Yes / No* Indicate yes if applicable:
	
Are you experiencing any of the following? (Please indicate when the symptoms began.)
 
 Nausea  Vomiting  Constipation  Weakness  Loss of appetite  Fever  Excessive fatigue

10	
Breakfast:
 
Lunch:
 
Dinner:
	
 Fruit juice: Yes / No* Indicate yes if applicable:
 
 Vitamin Yes / No* Indicate yes if applicable:
	
Sleep duration: Activity:
 
Are you experiencing any of the following? (Please indicate when the symptoms began.)
 
 Nausea  Vomiting  Constipation  Weakness  Loss of appetite  Fever  Excessive fatigue

11	
Breakfast:
 
Lunch:
 
Dinner:
	
 Fruit juice: Yes / No* Indicate yes if applicable:
 
 Vitamin Yes / No* Indicate yes if applicable:
	
Sleep duration: Activity:
 
Are you experiencing any of the following? (Please indicate when the symptoms began.)
 
 Nausea  Vomiting  Constipation  Weakness  Loss of appetite  Fever  Excessive fatigue

Signature of officer after filling out form:

Initials:

Date:

SAMPLE

Research Number:		Respondent's initials: []	
12	Breakfast:	 Fruit juice: Yes / No* Indicate yes if applicable:	Sleep duration: Activity: Are you experiencing any of the following? (Please indicate when the symptoms began.)  Nausea  Vomiting  Constipation  Weakness  Loss of appetite  Fever  Excessive fatigue
	Lunch:	 Vitamin Yes / No* Indicate yes if applicable:	
	Dinner:		
13	Breakfast:	 Fruit juice: Yes / No* Indicate yes if applicable:	Sleep duration: Activity: Are you experiencing any of the following? (Please indicate when the symptoms began.)  Nausea  Vomiting  Constipation  Weakness  Loss of appetite  Fever  Excessive fatigue
	Lunch:	 Vitamin Yes / No* Indicate yes if applicable:	
	Dinner:		
14	Breakfast:	 Fruit juice: Yes / No* Indicate yes if applicable:	Sleep duration: Activity: Are you experiencing any of the following? (Please indicate when the symptoms began.)  Nausea  Vomiting  Constipation  Weakness  Loss of appetite
	Lunch:	 Vitamin Yes / No* Indicate yes if applicable:	
	Dinner:		

Signature of officer after filling out form:

Initials:

Date:

SAMPLE

Research Number:		Respondent's initials: []	
			 Fever  Excessive fatigue
15	Breakfast:	 Fruit juice: Yes / No* Indicate yes if applicable:	Sleep duration: Activity:
	Lunch:	 Vitamin Yes / No* Indicate yes if applicable: 	Are you experiencing any of the following? (Please indicate when the symptoms began.)  Nausea  Vomiting  Constipation  Weakness  Loss of appetite  Fever  Excessive fatigue
	Dinner:		
16	Breakfast:	 Fruit juice: Yes / No* Indicate yes if applicable:	Sleep duration: Activity:
	Lunch:	 Vitamin Yes / No* Indicate yes if applicable: 	Are you experiencing any of the following? (Please indicate when the symptoms began.)  Nausea  Vomiting  Constipation  Weakness  Loss of appetite  Fever  Excessive fatigue
	Dinner:		
17	Breakfast:	 Fruit juice: Yes / No* Indicate yes if applicable:	Sleep duration: Activity:
	Lunch:	 Vitamin Yes / No* Indicate yes if applicable: 	Are you experiencing any of the following? (Please indicate when the symptoms began.)  Nausea  Vomiting

Signature of officer after filling out form:

Initials:

Date:

SAMPLE

Research Number:		Respondent's initials: []	
	Dinner:	 	 Constipation  Weakness  Loss of appetite  Fever  Excessive fatigue
18	Breakfast:	 Fruit juice: Yes / No* Indicate yes if applicable:	Sleep duration: Activity:
	Lunch:	 Vitamin Yes / No* Indicate yes if applicable:	Are you experiencing any of the following? (Please indicate when the symptoms began.)  Nausea  Vomiting  Constipation  Weakness  Loss of appetite  Fever  Excessive fatigue
	Dinner:	 	
19	Breakfast:	 Fruit juice: Yes / No* Indicate yes if applicable:	Sleep duration: Activity:
	Lunch:	 Vitamin Yes / No* Indicate yes if applicable:	Are you experiencing any of the following? (Please indicate when the symptoms began.)  Nausea  Vomiting  Constipation  Weakness  Loss of appetite  Fever  Excessive fatigue
	Dinner:	 	
20	Breakfast:	 Fruit juice: Yes / No* Indicate yes if applicable:	Sleep duration: Activity:
	Lunch:	 Vitamin	Are you experiencing any of the following? (Please

Signature of officer after filling out form:

Initials:

Date:

SAMPLE

Research Number:		Respondent's initials: []	
	Dinner:	 Yes / No* Indicate yes if applicable:	indicate when the symptoms began.)  Nausea  Vomiting  Constipation  Weakness  Loss of appetite  Fever  Excessive fatigue
21	Breakfast:	 Fruit juice: Yes / No* Indicate yes if applicable:	Sleep duration: Activity:
	Lunch:	 Vitamin Yes / No* Indicate yes if applicable:	Are you experiencing any of the following? (Please indicate when the symptoms began.)  Nausea  Vomiting  Constipation  Weakness  Loss of appetite  Fever  Excessive fatigue
	Dinner:		
22	Breakfast:	 Fruit juice: Yes / No* Indicate yes if applicable:	Sleep duration: Activity:
	Lunch:	 Vitamin Yes / No* Indicate yes if applicable:	Are you experiencing any of the following? (Please indicate when the symptoms began.)  Nausea  Vomiting  Constipation  Weakness  Loss of appetite  Fever  Excessive fatigue
	Dinner:		
23	Breakfast:	 Fruit juice: Yes / No*	Sleep duration: Activity:

Signature of officer after filling out form:

Initials:

Date:

SAMPLE

Research Number:	Respondent's initials: []
------------------	---

	
Lunch:
 
Dinner:
	
Indicate yes if applicable:
 
 Vitamin Yes / No* Indicate yes if applicable:
 

	
Are you experiencing any of the following? (Please indicate when the symptoms began.)
 
 Nausea  Vomiting  Constipation  Weakness  Loss of appetite  Fever  Excessive fatigue

24	
Breakfast:
 
Lunch:
 
Dinner:
	
 Fruit juice: Yes / No* Indicate yes if applicable:
 
 Vitamin Yes / No* Indicate yes if applicable:
 

	
Sleep duration: Activity:
 
Are you experiencing any of the following? (Please indicate when the symptoms began.)
 
 Nausea  Vomiting  Constipation  Weakness  Loss of appetite  Fever  Excessive fatigue

25	
Breakfast:
 
Lunch:
 
Dinner:
	
 Fruit juice: Yes / No* Indicate yes if applicable:
 
 Vitamin Yes / No* Indicate yes if applicable:
 

	
Sleep duration: Activity:
 
Are you experiencing any of the following? (Please indicate when the symptoms began.)
 
 Nausea  Vomiting  Constipation  Weakness  Loss of appetite  Fever  Excessive fatigue

Signature of officer after filling out form:

Initials:

Date:

SAMPLE

Research Number:		Respondent's initials: []	
26	Breakfast:	 Fruit juice: Yes / No* Indicate yes if applicable:	Sleep duration: Activity: Are you experiencing any of the following? (Please indicate when the symptoms began.)  Nausea  Vomiting  Constipation  Weakness  Loss of appetite  Fever  Excessive fatigue
	Lunch:	 Vitamin Yes / No* Indicate yes if applicable:	
	Dinner:		
27	Breakfast:	 Fruit juice: Yes / No* Indicate yes if applicable:	Sleep duration: Activity: Are you experiencing any of the following? (Please indicate when the symptoms began.)  Nausea  Vomiting  Constipation  Weakness  Loss of appetite  Fever  Excessive fatigue
	Lunch:	 Vitamin Yes / No* Indicate yes if applicable:	
	Dinner:		
28	Breakfast:	 Fruit juice: Yes / No* Indicate yes if applicable:	Sleep duration: Activity: Are you experiencing any of the following? (Please indicate when the symptoms began.)  Nausea  Vomiting  Constipation  Weakness  Loss of appetite
	Lunch:	 Vitamin Yes / No* Indicate yes if applicable:	
	Dinner:		

Signature of officer after filling out form:

Initials:

Date:

SAMPLE

Research Number:	Respondent's initials: []
------------------	---

		 Fever  Excessive fatigue
--	--	--

*cross out what is unnecessary

Signature of officer after filling out form: Initials: Date:
